9.0 TREATMENT/INTERVENTION PLAN

Patients will be randomized into one of 3 arms as described above, and will be followed up for 24 months. Patients will be encouraged to have sexual relations, when comfortable after RP. This is 'usual care'. The use of nightly sildenafil citrate and intracavernosal injection therapy is considered investigational, and this study is designed to define whether one, or the other, or a combination of these strategies, should become 'usual care'. Patients routinely complete questionnaires after surgery, the only additional requirement for patients will be the completion of a pill diary/sexual encounter diary, to delineate the exact utilization of medication for sexual relations as well as document all study medication use. Patients will be followed at 3, 6, 9, 12, 18, and 24 months. Intervention (placebo, sildenafil or injection) will be used for 12 months. Patients will have their sildenafil dose adjusted according to their erectile response and side effects (listed in section 11.0). For example, for men responding robustly to sildenafil 100 mg may be down-titrated to 50 mg or 25 mg. Likewise, men who have side effects (as outlined in Section 11.0) at sildenafil 100 mg will be down-titrated to 50 mg or 25 mg. If patients are experiencing side effects from daily 50 mg dose, they may downtitrated to 25mg, by halving the pill. Intra-cavernosal injection agent dose will be downtitrated for penetration hardness erection lasting for greater than 60 minutes or if any side effects are seen, as listed in section 11.0. Trimix and Bimix have a 1 month expiration date. Combination Therapy Arm patients will be prescribed a total of 3 vials of Trimix or Bimix at their 2nd injection training visit and 3, 6, and 9 month protocol visits. The patient will pick up 1 vial after their appointment and outpatient pharmacy will arrange to have the remaining 2 vials shipped to the patient at 1 month intervals to cover their treatment plan for a total of 3 months.

IRB PB

IRB#: 09-005 A(10)

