10.0 EVALUATION DURING TREATMENT/INTERVENTION

Before treatment (baseline) and 3, 6, 9, 12, 18, and 24 months visits, patients will be evaluated in clinic. Patients will be asked for any adverse events, since last visit, and will be given the International Index of Erectile Function (IIEF) validated questionnaire (Appendix A), pill diary/sexual encounter diary (Appendix B), and drug accountability (Appendix E). The pill diary/sexual encounter diary (Appendix B) and drug accountability (Appendix E) will be completed at home. Patients will be given enough diaries to capture at least 18 sexual attempts. At each study visit, the paperwork will be collected and the patient given new diaries. The assigned research professional will review paperwork for any mistakes or inconsistencies before patient leaves clinic. Patient's liver functions will be tested and sitting and standing blood pressure, and pulse will be completed at 3, 6, 9, 12, 18, and 24 months visits.

The IIEF is the gold standard questionnaire in erectile function assessment. It has been validated in numerous languages and has been used for more than a decade now in this field. It has 5 domains, one of which is erectile function (the others are libido, orgasm, intercourse satisfaction and overall satisfaction). Each question is scored on a 5 point scale, where '5' is 'always' and '1' is 'never' and '3' is 'half the time', in response to questions pertaining to obtaining and maintaining erection. The pill diary/sexual encounter diary will ask patients to record sexual encounters, whether sildenafil or penile injections was used, at what dose, whether vaginal penetration occurred, and how they rate their erectile rigidity as well as all study medication use.

At 12 months, patients will be instructed to discontinue treatment (that is, either daily pill use or injection therapy). They will be permitted to use PRN sildenafil or injections for the purpose of sexual relations, prescribed through treating physician. Follow up will continue for 24 months in total. The administration of the study medications will be monitored by the research pharmacy staff to ensure compliance with the protocol, as well as maximizing patient safety.

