11.1 TOXICITIES/SIDE EFFECTS

The side effects from each pharmacologic intervention are listed below. Side effects will be assessed at each follow-up visit by direct questioning of patients.

Sildenafil:

- 1. Headache 15%
- 2. Flushing of the face 10%
- 3. Gastrointestinal upset 7%
- 4. Temporary visual changes 2%
- 5. Nasal congestion 4%.

(RB PB

IRB#: 09-005 A(10)

Trimix and Bimix:

- 1. PGE1 can induce pain (in up to 30% of patients taking PGE1)
- 2. Fibrotic reactions (i.e. subcutaneous nodules, intracavernosal fibrotic areas, have been reported). In most cases, penile nodules that occur with injection therapy disappear within a few months of stopping.
- 3. Ecchymosis
- 4. Priapism (0.5-5%). (If not treated right away, permanent damage to the penis could occur). Of note, the incidence of priapism in [name] practice is less than 0.15%.

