14.3 Data Analysis

Summary statistics will be calculated, by group, for age, surgery (open or laparoscopic), tumor characteristics (stage, grade, PSA), baseline erectile function and quality of life scores. Compliance and off-study use of medications for erectile function will be described by group and follow-up time. Biochemical recurrences will be described separately by group using Kaplan-Meier methods.

The primary analysis will compare the erectile function domain score of the IIEF at 24 months. Secondary endpoints include:

- 1. EF scores at other time-points
- 2. The proportion of patients who have normalization of their erectile function, defined as a score of 26 or greater on the EF domain of the IIEF at any point during the study
- 3. Time for response to sildenafil (as defined by diary)
- 4. Time to return of spontaneous functional erections (as defined by diary)

(RB PB

IRB#: 09-005 A(10)

The primary comparison and secondary comparison 1 will be made by analysis of covariance with baseline score and randomization strata as the covariates. Secondary endpoint 2 will be compared by Fisher's exact test. Secondary endpoints 3 and 4 will be compared between groups by log rank. Three pairwise comparisons will be made: nightly sildenafil vs. PRN sildenafil; combination treatment vs. PRN sildenafil; nightly sildenafil vs. combination treatment.

As an additional analysis, we will model EF scores over time using Generalized Estimating Equations with time, treatment, time by treatment and baseline score as predictors. Treatment will be entered as two dummy variables: nightly sildenafil (coded 0 in the PRN group and 1 otherwise) and injection therapy (coded 1 in the combination group and 0 otherwise).

All analyses will be on the intention-to-treat principle with patients analyzed in their randomized groups regardless of the treatment actually received. All comparisons between combination and PRN sildenafail, and between nightly and PRN sildenafil, will use a 2.5% alpha; all comparisons between the two treatment arms will use a 90% non-inferiority bound.

The nature, severity and day of onset of adverse effects will be described along with assessment of causality.

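### Section 14.3 applies intention-to-treat to every analysis, with no safety exception, exposed denominator or on-treatment window, so injection-specific harm rates could be diluted

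*Combined protocol and SAP*

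**What the plan says.** Section 14.3 (Data Analysis) sets one rule for the analysis population: "All analyses will be on the intention-to-treat principle with patients analyzed in their randomized groups regardless of the treatment actually received". The next paragraph holds the only safety analysis in the plan: "The nature, severity and day of onset of adverse effects will be described along with assessment of causality". No safety population, exposed denominator or treatment-emergent window is defined there or elsewhere.

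The periods of treatment and of safety follow-up differ:

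- Section 9.0: "Intervention (placebo, sildenafil or injection) will be used for 12 months".
- Section 10.0: "Follow up will continue for 24 months in total".
- Section 11.1: "Side effects will be assessed at each follow-up visit by direct questioning of patients". The visit table in Section 1.1 lists adverse event assessment at 3, 6, 9, 12, 18 and 24 months.
- Section 10.0, on what men may do after stopping at month 12: "They will be permitted to use PRN sildenafil or injections for the purpose of sexual relations, prescribed through treating physician". This permission is not limited by arm.

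The plan also provides information that could resolve the matter. Section 14.3 says: "Compliance and off-study use of medications for erectile function will be described by group and follow-up time". Under Section 10.0 the diary records study medication use and, for each sexual encounter, whether sildenafil or an injection was used and at what dose. A drug accountability form is collected as well.

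**The concern.** Analysing men as randomised protects the efficacy comparison. For harms it answers a different question from the one a man considering injections would ask, which is how often men who inject have pain, priapism or fibrosis. Section 11.1 itself quotes pain as a rate among men taking PGE1, and a rate per randomised man cannot be set against that figure.

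Assignment and exposure can separate in this trial. Under Section 4.3, men who consent before surgery are randomised immediately after it. Under Section 4.4, the combination arm takes sildenafil alone for about two weeks before the first injection. Section 18.1 lets participants refuse an intervention or withdraw. In the other direction, men from the oral arms may inject off study in year two while adverse events are still being collected.

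Section 14.2 justifies the non-inferiority comparison by the premise that injections are harder to tolerate than tablets. The adverse-effect data are the trial's own evidence on that premise, so they should show injection harms clearly.

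**Working it through.** No figure in the plan bears directly on this point, so there is none to reproduce. The stated power rests on arm sizes, SD, effect size or margin, and error rates (Section 14.2). None of these involves the safety population.

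**Inputs**

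- Combination arm: 80 men (Section 14.2).
- Pain: up to 30% of men taking PGE1 (Section 11.1). This is an upper limit.
- Priapism: 0.5% to 5% (Section 11.1), with a local-practice figure below 0.15% also given there.
- Share of the combination arm that never injects, *u*: not in the documents. Assumed 0%, 10%, 20% and 30%.
- Share of an oral arm that injects off study in year two, *w*: not in the documents. Assumed 10%, 20% and 30%.

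**Step 1: never-injectors kept in the denominator.** Reported rate = *r* × (1 − *u*), where *r* is the rate among users.

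| *u* | Men who inject | Expected pain cases at 30% | Pain per 80 randomised | Pain per man injecting | Priapism per 80, if 5% among users |
|---|---|---|---|---|---|
| 0% | 80 | 24.0 | 30% | 30% | 5.0% |
| 10% | 72 | 21.6 | 27% | 30% | 4.5% |
| 20% | 64 | 19.2 | 24% | 30% | 4.0% |
| 30% | 56 | 16.8 | 21% | 30% | 3.5% |

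The exposed denominator restores the rate, for example 19.2/64 = 30%. With *u* = 0 there is no dilution. For priapism the change is small in men: at 5% and *u* = 20%, 80 × 0.05 = 4.0 expected cases become 64 × 0.05 = 3.2.

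**Step 2: year-two injections in an oral arm.** If a share *w* of an oral arm injects after month 12 and has pain at the same 30%, the randomised-group rule assigns 0.30 × *w* to that arm: 3%, 6% or 9% for *w* = 10%, 20% or 30%.

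**Step 3: both together.** With *u* = *w* = 20%, and assuming the never-injectors do not start in year two, the arms read 24% and 6%. The gap is 18 percentage points. With *u* = *w* = 0 it would be 30 − 0 = 30 points.

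**Step 4: the window.** Planned treatment covers 12 of 24 months of collection (50%). After the two-week lead-in, planned injections cover about 52 − 2 = 50 of 104 weeks (48%). About half of the collection period is therefore one in which use is off study.

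**The case against.** The strongest reply is that the ingredients for a correct table are already planned. Day of onset separates events before and after month 12, causality is assessed, and off-study use is described by group and time. All of this stands, and it is why the remedy is cheap. It does not commit the analysis to linking events with exposure: off-study use is described in one sentence, adverse effects in another, and nothing joins them.

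A second reply is that the intention-to-treat sentence opens a paragraph on alpha and the non-inferiority bound, so it may be meant for comparisons only. That is a fair reading, but the words cover all analyses. If the rule does not reach safety, the plan states no safety population at all, so a sentence is needed either way.

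Third, the shares are assumed and the rates are upper limits. Section 4.4 has the first two injections given in clinic, so few men may never inject. This stands. Dilution is possible but not certain, and year-two use could also add events to the combination arm.

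Some stronger readings are tempting but unsupported:

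- A reader might infer that adverse effects will be pooled over all 200 men because that sentence does not repeat a split by group. Nothing says to pool, and the intention-to-treat sentence, if it governs, places men in their randomised groups.
- A reader might extend the point to sildenafil harms. Controls receive open-label sildenafil 100 mg as needed (Section 4.2), so that contrast is blurred by design and a different analysis set would not remove the blur.
- Section 11.1 says "In most cases, penile nodules that occur with injection therapy disappear within a few months of stopping", and a reader might infer that persistence of nodules at month 24 can be tabulated. The documents do not show that resolution is recorded; the adverse event form is listed as Appendix D but not reproduced.

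**Conclusion.** The gap is real and minor. Followed literally, Section 14.3 keeps never-injectors in the denominator for injection harms and counts year-two off-study injection events in the randomised arm, so injection-specific rates could be diluted and the arms drawn together. The size is proportional to non-exposure: none at 0%, and one fifth of the rate at 20% (30% reads 24%). It rests on assumed shares and on the upper-limit rates in Section 11.1.

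A reader might infer that the choice between the active arms is at risk. It is not. In Section 14.2 lower tolerability is a premise, and the decision rule is the three-point margin on the erectile function score. The primary analysis, the power and the non-inferiority decision are unchanged; what changes is how informative the injection-harm report is.

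**What to change.** In Section 14.3:

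1. Limit the intention-to-treat sentence to efficacy analyses.
2. State that adverse effects are summarised by arm among men who took at least one dose of study drug (placebo tablets included), and injection effects among men with at least one injection. Exposure is taken from the diary and drug accountability records.
3. Show months 0-12 and 12-24 separately, with year-two events cross-classified by recorded off-study use.
4. Keep a randomised-group table of adverse effects alongside.

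The cost is a few sentences and some extra tables from data already planned for collection. The drawback is that exposed sets are not strictly randomised comparisons, which is the reason for item 4. No treatment rule or visit needs to change.

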14.1 BIOSTATISTICS

14.2 Sample Size

For each endpoint we will conduct three analysis:

- 1. A comparison of nightly sildenafil to PRN sildenafil with an alpha of 2.5%
- 2. A comparison of combination treatment to PRN sildenafil with an alpha of 2.5%
- 3. A non-inferiority comparison between nightly sildenafil and combination treatment: in this analysis, nightly sildenafil will be considered non-inferior to combination treatment if the upper bound of a 90% confidence interval for the difference between groups does not include combination treatment being at least three points superior to nightly sildenafil.

(RB PB

Amended: 02/12/13

- 15 -

IRB#: 09-005 A(10)

Our rationale is for the different comparisons is as follows. We want to know whether the two active arms (nightly sildenafil and combination treatment) are superior to control (PRN sildenafil). We will therefore test each against control using an alpha half of the conventional value to account for multiple testing. Furthermore, combination treatment, which involves penile injection, is less tolerable for patients than nightly sildenafil, which only involves oral medication. Therefore unless nightly sildenafil is demonstrably inferior to combination treatment, we will recommend that injections are not required. Hence we will conduct a non-inferiority comparison between the two active arms.

Our primary endpoint is the IIEF-EF at 24 months. Based on previous studies, we estimate that the SD for the IIEF-EF will be 9 points. Prior data at MSKCC suggest that the correlation between baseline and follow-up IIEF-EF will be small enough as to have a negligible effect on variance. The minimum, clinically significant difference between active and control arms is 6 points based on our clinical experience and discussion held with [name] the designer of the IIEF. If we obtain data from 80 patients on each of the two active arms (nightly sildenafil and combination therapy) and 40 patients on the control arm (PRN sildenafil), we will have 89% power for the comparison between active and control and 80% power for the non-inferiority comparison between active arms.

MSKCC surgeons do approximately 850 radical prostatectomies per year. We estimate that 50% of patients will be eligible for the study. Assuming that 25% - 33% of eligible patients enroll, we should complete accrual within 18-24 months.

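### Nightly v combination is to be tested for non-inferiority on every endpoint, but the only margin fits IIEF-EF scores; and the 90% bound is not stated to be one-sided

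*Combined protocol and SAP*

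**What the plan says.** Section 14.2 opens with "For each endpoint we will conduct three analysis". The third analysis is a non-inferiority comparison of the two active arms. The margin is set by requiring that the interval "does not include combination treatment being at least three points superior to nightly sildenafil". The limit to be used is described as the "upper bound of a 90% confidence interval for the difference between groups", with no word on whether it is one- or two-sided. Section 14.2 then claims "80% power for the non-inferiority comparison between active arms", with 80 patients per active arm and an SD of 9 points.

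Section 14.3 repeats the rule without limiting it to the score: "all comparisons between the two treatment arms will use a 90% non-inferiority bound". The endpoints it covers are:

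- the IIEF-EF score at 24 months (primary) and at other times (secondary 1), by analysis of covariance with baseline score and randomization strata;
- the proportion reaching an EF score of 26 or more at any point (secondary 2): "Secondary endpoint 2 will be compared by Fisher's exact test";
- two diary-based times, to sildenafil response and to spontaneous functional erections: "Secondary endpoints 3 and 4 will be compared between groups by log rank".

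Section 15.3 stratifies randomization by surgeon (three strata). The Fisher test, the log-rank test and the GEE model in section 14.3 do not use those strata.

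**The concern.** A non-inferiority claim needs an effect measure, an interval and a margin on the same scale. The plan gives all three for IIEF-EF scores. For secondary endpoints 2 to 4 it gives none: a three-point margin has no meaning for a proportion or a time to event, and Fisher's exact test and the log-rank test address no difference and do not themselves yield a bound. If a claim is still to be made, someone must choose a margin later. Men and staff know who is injecting, so that choice could be made with outcomes visible by arm.

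The second issue is the meaning of the 90% interval. A one-sided 90% bound and the upper limit of a two-sided 90% interval are different rules, and some primary results would be non-inferior under one and not under the other.

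Two smaller matters belong with these. The surgeon strata are used in one analysis and dropped in the others. And one secondary endpoint, "Time for response to sildenafil (as defined by diary"), may not be observed with equal opportunity in the two arms compared.

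**Working it through.** **1. The plan's own power figures (section 14.2: SD 9; 80, 80 and 40 patients; difference 6; margin 3).**

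- Active v PRN, two-sided alpha 2.5%: SE = 9 × √(1/40 + 1/80) = 1.743; power = Φ(6/1.743 − 2.241) = 88.5%. The stated 89% reproduces.
- Nightly v combination, true difference 0: SE = 9 × √(2/80) = 1.423.

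| Reading of the 90% bound | Power | Largest observed deficit still non-inferior |
|---|---|---|
| One-sided 90% bound | Φ(3/1.423 − 1.282) = 79.6% | 3 − 1.282 × 1.423 = 1.18 points |
| Limit of a two-sided 90% interval | Φ(3/1.423 − 1.645) = 67.8% | 3 − 1.645 × 1.423 = 0.66 points |

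Only the one-sided reading reproduces the stated 80%. An observed deficit between 0.66 and 1.18 points would be judged differently under the two readings.

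**2. How much an unstated margin matters (80 v 80, equal true rates, one-sided 90% bound).** The normalization and event rates here are assumptions. Section 3.0 cites related rates (spontaneous function in 30–80%, a 43% sildenafil responder rate, 27% v 4%, 67% v 20%), but none uses this trial's endpoint definitions.

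- Normalization at 30% to 50%: SE = √(2p(1 − p)/80) = 0.0725 to 0.0791. The bound lies 1.282 × SE = 9.3 to 10.1 percentage points from the estimate. A margin of (1.282 + 0.842) × SE = 15.4 to 16.8 points is needed for 80% power.
- Both arms truly at 50%: the chance of declaring non-inferiority is Φ(margin/0.0791 − 1.282), which is 49%, 73% and 89% for margins of 10, 15 and 20 points.
- Three points read as three percentage points: Φ(0.03/SE − 1.282) = 18% to 19%, so that reading would not rescue the rule.
- Times to event with 64 or 96 events (40% or 60% of 160): SE(log HR) = 2/√events = 0.250 or 0.204. The bound is the estimated hazard ratio divided by exp(1.282 × SE) = 1.38 or 1.30. A margin of exp(2.124 × SE) = 1.70 or 1.54 is needed for 80% power.

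**3. Leaving out the surgeon strata (active v PRN, 80 v 40, two-sided alpha 2.5%).** All surgeon differences and effects are assumed, and the endpoint 2 and log-rank figures come from simulation.

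- Endpoint 2, odds ratio 3.5, power:

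| Control rates by surgeon | Fisher | Unstratified score | Stratified Mantel-Haenszel |
|---|---|---|---|
| 30/30/30% | 79.3 | 81.5 | 81.8 |
| 25/30/35% | 77.9 | 80.3 | 81.3 |
| 20/30/40% | 74.7 | 77.1 | 79.9 |
| 15/30/50% | 66.5 | 69.5 | 76.9 |

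The gain from stratifying (Mantel-Haenszel minus score) is about 0, 1, 3 and 7 points. At odds ratio 2.5 it is 0.0, 1.3, 3.6 and 8.7. Size under the null is 2.4–2.5% for Mantel-Haenszel and 1.5–2.0% for Fisher.

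- Log rank, hazard ratio 2, unstratified v stratified: 59.9 v 59.5% with no surgeon differences, and 50.1 v 60.5% with the largest (25/40/60% with the event by 24 months).
- GEE, one-time-point approximation, surgeon means 2 or 3 points either side of the middle one: 88.9 v 89.6% and 89.4 v 90.9%.

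**4. Time to sildenafil response.** Sections 4.2 and 4.4 provide on-demand sildenafil 100 mg in the nightly arm. Combination patients take 50 mg on the four non-injection nights and may use injections for sexual relations. Section 10.0 permits PRN sildenafil or injections after treatment stops at 12 months. Nightly patients may therefore have more recorded occasions on which to respond to sildenafil. The documents give no figure from which to size this.

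**The case against.** The strongest objection is that section 14.3 merely sets error levels, and that the Fisher and log-rank tests can be run as written. They can, as tests of difference. But section 14.2 names the non-inferiority analysis itself for each endpoint, so the plan promises more than those tests deliver.

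It is also fair to say that the stated power largely settles the one-sided reading, so that this is a matter of wording. That stands. The sentence still defines the primary decision rule and should not have to be inferred from a power figure. The 49%, 73% and 89% are ordinary power at illustrative margins; they show sensitivity to an unstated choice, not that anyone would misuse it.

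Leaving out the strata costs power under assumed surgeon differences and does not inflate false positives. It is an improvement at almost no cost, not a correction of an invalid test.

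On time to sildenafil response, a reader might infer a large bias toward nightly treatment. The documents do not support a size. Section 4.3 expects very few men to respond to any drug of this class in the first nine months, which limits how much unequal access can matter. Nor is a finding of non-inferiority wrong when true recovery is equal. Section 14.3 already promises to describe compliance and off-study medication use by group, which covers part of the concern.

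**Conclusion.** The stated non-inferiority rule cannot be carried out for secondary endpoints 2 to 4, because no margin, effect measure or interval exists for them. This follows from the text and needs no assumed rate. It affects secondary conclusions only.

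A reader might infer that the primary non-inferiority analysis is undefined, or that the recommendation on injections rests on the affected endpoints. Neither is supported: the primary comparison has a margin, a measure and an interval, and no section ties the recommendation to endpoints 2 to 4.

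The unclear sidedness does reach the primary comparison: 79.6% v 67.8% power, and a critical deficit of 1.18 v 0.66 points. It would be too strong to call the trial underpowered on this ground, since the planned power matches the one-sided bound. These figures rest on the plan's SD of 9, 80 evaluable patients per arm and no true difference.

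The surgeon strata are worth about 0 to 7–9 points of power for endpoint 2, depending on assumed surgeon differences. The unequal access to sildenafil is a caveat of unknown size. Overall the plan should be changed, but the primary analysis stands.

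**What to change.** 1. Limit non-inferiority claims to IIEF-EF scores. For nightly v combination on endpoints 2 to 4, report a surgeon-stratified risk difference and hazard ratios with two-sided 90% confidence intervals, as estimates and without a non-inferiority claim.
2. State that the 90% non-inferiority bound is one-sided, which matches the planned 80% power.
3. Use a surgeon-stratified Mantel-Haenszel test for endpoint 2 and a surgeon-stratified log-rank test for endpoints 3 and 4, and add surgeon to the GEE.
4. Attach a caveat to time to sildenafil response for nightly v combination, and report sildenafil-assisted attempts by arm from the diary.

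The cost is SAP wording and a little analysis code. Surgeon is already recorded for randomization, and section 10.0 has the diary record sildenafil or injection use at each encounter. No new patients, visits or data are needed, and the stratified tests lose essentially nothing if surgeons do not differ.
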